## Protocol

This study aims to investigate the effects of time-of-day and menstrual cycle phase on tier 2 female's cognitive and strength performance through several measures. The independent variables for this study are (i) time-of-day (three levels: 07:00, 12:00, and 18:00 h) and (ii) menstrual cycles phase in eumenorrheic females (two levels: low levels of progesterone (phase 1) and high levels of progesterone (phase 4) ( $>16\text{nmol L}^{-1}$ ; Verhagen *et al.*, 2025)). The dependent variables of this study include muscle strength, measured across three domains (maximal handgrip strength, flight time and height performing CMJ and SJ, and maximal lower limb strength), and executive function using a modified version of Eriksen's original Flanker task, (Koch and Krenn, 2021), and electroencephalography (EEG) alpha wave activity, measured with an Enobio 8 EEG system (Neuroelectrics/Cambridge/MA). Each measure will have at least one cross validation measure, to ensure greater validity in our findings.

An a-priori analysis was conducted using G\*Power version 3.1.9.6 for this study (Faul *et al.* 2007); chosen due to the intention to analyse the data using a MANOVA repeated measures within factors statistical test. The sample size for this study was determined based on a medium effect size ( $f=0.25$ ), using a statistical power of 80% and an alpha value of 0.05. This study involves one group (tier 2 females partaking in sports) with two independent variables of time of day (07:00, 12:00, and 18:00 h) and menstrual cycle phase (highest and lowest levels of progesterone). G\*Power indicated a minimum sample size of 24, however, to account for any potential data loss or dropouts, this study will aim to collect data from 30 participants.

Participants will be recruited via opportunity sampling with the use of posters placed around Lancaster University campus, online advertisements on social media platforms and through word of mouth. For individuals to participate, they must meet the extensive eligibility criteria to ensure that this study tests the effects of time-of-day and menstrual cycle phases on tier 2 female cognitive and strength performance. Participants must fit the following criteria:

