**Research design**

[figure not shown]
Screening and familiarisation visit including the 'Screening questionnaire pack', and test familiarisation of executive function flanker task and muscle strength test battery

2 experimental sessions i) Phase 1 and ii) Phase 4

Retiring by 23:00 the night before testing and waking at 06:00 h the day of testing

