Venipuncture of the arm would then be performed to draw blood from the participants. The blood samples would be collected in several vacutainers (gold topped for Oestrogen, progesterone and hsCRP, and purple top for inflammatory markers) with a small volume extracted and placed on ProWipes pads where the participant's blood can be drawn up in a capillary tube for **glucose and lactate** analysis using a blood analyser (Biosen C-Line GP+/EKF/Barleben, Germany). This measure will only be performed at the morning visit to consider blood glucose and lactate levels after the overnight fast. The remaining **blood samples** collected in vacutainers would be stored at -80°C before carrying out various assays, according to manufacturer's guidelines, to measure progesterone (P), oestradiol (E2) and Interleukin (IL-6), Tumour necrosis factor (TNF $\alpha$ ) and high sensitivity C reactive protein (hsCRP). Blood analysis of progesterone and oestrogen would be carried out in duplicate using commercially available serum and plasma enzyme linked immunosorbent assays (ELISA). The blood analysis would act to confirm correct phase identification during testing, with the exclusion of participants occurring after testing due to E2 or P levels not matching those defined for Phase 1 and 4 above.

*Table 1: summary table of proteins measured, their biofluid and the purpose of the measurement*

	Biofluid	Assay	Purpose of measure
Progesterone	Serum	ELISA	As a confirmation of phase of participant's cycle.
Oestradiol	Serum	ELISA	As a confirmation of phase of participant's cycle.
Luteinising hormone	Urine	Easy@Home, Easy Healthcare Corporation, IL, USA	Carried out 5 days prior to expected the LH surge which occurs 24-48 hours prior to ovulation to determine when ovulation will fall.
IL-6	Serum and Plasma	LEGENDplex Human inflammation panel 1	To measure key inflammatory markers to determine a possible relationship between inflammation and the menstrual cycle/time-of-day, resulting in possible discrepancies in strength and cognitive measures.
TNF- $\alpha$	Serum and plasma	LEGENDplex Human inflammation panel 1	To measure key inflammatory markers to determine a possible relationship between inflammation and the menstrual cycle/time-of-day, resulting in possible discrepancies in strength and cognitive measures.

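### The planned repeated-measures MANOVA discards a participant's whole record for an outcome when one session is missing; a mixed model would keep the valid sessions, with a modest gain in power

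*Protocol*

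**What the plan says.** The opening Protocol section names the analysis and ties the sample size to it: G*Power was chosen because of "the intention to analyse the data using a MANOVA repeated measures within factors statistical test". The inputs are a medium effect (f = 0.25), "using a statistical power of 80% and an alpha value of 0.05", and a single group. The result is a minimum of 24, raised to 30: "to account for any potential data loss or dropouts, this study will aim to collect data from 30 participants". No expected loss rate is given.

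The within-participant factors are "time-of-day (three levels: 07:00, 12:00, and 18:00 h") and menstrual cycle phase, run as "2 experimental sessions i) Phase 1 and ii) Phase 4". That makes 3 × 2 = 6 cells for the Flanker and EEG outcomes. The test day protocol leaves the strength tests out at 12:00, so strength has 2 × 2 = 4 cells. The paragraph before it says that the same battery is run at every time. The two statements need reconciling, and the count of four rests on the more specific one.

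The blood-sampling paragraph of the Experimental protocol describes a separate loss, at participant level: "with the exclusion of participants occurring after testing due to" hormone levels that do not match the phase definitions.

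**The concern.** A standard repeated-measures MANOVA works on each participant's full vector of measurements. One unusable EEG recording or one missed return visit removes that participant from the outcome, together with up to five valid sessions. The six spare places are counted in participants, but under this test they can be used up by single sessions. Each test day has three visits between 07:00 and 18:00, and each visit includes two EEG recordings and a two-part Flanker task, so isolated session losses are plausible.

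What is at stake is valid data thrown away in a small study, and a complete-case set that may fall below the stated minimum because of the choice of test. Complete cases may also differ from the rest, for example in how well they tolerate long test days.

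**Working it through.** **Inputs.** From the protocol: f = 0.25, alpha 0.05, power 80%, one group, minimum 24, target 30, six cells (four for strength). Assumed: a correlation rho = 0.5 between repeated measures, which the protocol does not state; independent session losses; and the loss rates themselves.

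**1. The plan's own figure.** For a one-group repeated-measures MANOVA with m cells, the F test has df1 = m − 1, df2 = N − m + 1 and noncentrality N·m·f²/(1 − rho). With m = 6, N = 24 and rho = 0.5, these are df 5 and 19 and noncentrality 24 × 6 × 0.0625/0.5 = 18. Power is 0.825 at N = 24 and 0.799 at N = 23, so the minimum of 24 reproduces. The settings are not uniquely identified: m = 3 with rho = 0.6 also gives 24. For m = 6 the required N is 30, 27, 24, 20 and 17 at rho 0.3, 0.4, 0.5, 0.6 and 0.7.

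**2. Session loss that leaves 24 complete of 30.** With k cells and independent loss p per session, solve 30(1 − p)^k = 24, so p = 1 − 0.8^(1/k). The simple count is six participants losing one session (or day) each.

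| Pattern of loss | p from formula | By count |
|---|---|---|
| Flanker/EEG, scattered sessions (k = 6) | 3.65% | 6/180 = 3.3% |
| Strength, scattered sessions (k = 4) | 5.4% | 6/120 = 5.0% |
| Whole test days (k = 2) | 10.6% | 6/60 = 10% |
| Whole participants | 20% | 6/30 = 20% |

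**3. Complete cases and power, six-cell outcomes.** The number of complete cases is binomial with size 30 and probability (1 − p)^6. Expected power averages the power from step 1 over that distribution.

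| Session loss | Expected complete | P(at least 24) | Expected power |
|---|---|---|---|
| 2% | 26.6 | 95% | 88% |
| 3% | 25.0 | 78% | 84% |
| 3.65% | 24.0 | 61% | 82% |
| 5% | 22.1 | 28% | 76% |

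At 22 complete cases power is 0.77 with rho 0.5, 0.68 with rho 0.4 and 0.87 with rho 0.6.

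**4. Other patterns at 5% loss.** Four strength cells leave 24.4 expected complete cases and a 68% chance of at least 24. Independent loss of whole days leaves 27.1 and 98%. For strength, 24 is not itself the 80% point: with m = 4 and rho = 0.5 the same formula requires 26, and power at 24 is 0.76.

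**5. Data kept.** If six participants each lose one of six sessions, the MANOVA uses 24 × 6 = 144 of 180 sessions. A mixed model uses 180 − 6 = 174.

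**The case against.** The strongest case on the other side is that the test is valid, agrees with the sample-size method, and leaves the covariance unstructured. The handling of partly missing sessions may be set out in a statistical analysis plan that is not shown. The power loss is also small: at the very point where the allowance is used up in expectation, average power is still about 82%. All of this stands and limits the weight of the point. It does not remove it, because the protocol fixes the test by name and the test itself causes the deletion.

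Three stronger readings are tempting, and the document does not support them.

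- *That losing under 4% of sessions exhausts the allowance in general.* This holds only for the six-cell outcomes with scattered, independent losses. Sessions are grouped three to a day, and loss of whole days moves the figure to about 10%.
- *That the allowance was set as 20% loss of participants.* Six of 30 is 20%, but the protocol states no percentage, and its wording covers data loss as well as dropout.
- *That the MANOVA discards the valid Phase 1 day of a participant whose Phase 4 hormone check fails.* The exclusion rule removes that participant under any model. The rule can also be read as defining the eumenorrheic population. Using the verified day would be a separate change to that rule, and such a participant would add little to the within-person phase contrast.

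**Conclusion.** The concern holds in a limited form. The named test drops a participant from an outcome for one missing cell. For Flanker and EEG, scattered loss of about 3.3–3.7% of sessions is enough to reduce 30 participants to 24 complete cases; for strength the figure is about 5.0–5.4%, and for whole-day loss about 10%. Expected power on the six-cell outcomes stays above 80% up to the 3.65% point and falls to about 76% at 5% loss. These figures assume independent losses and rho = 0.5, and the loss rates are illustrative. The waste of data is avoidable at little cost, so the change is worth making, but this is a matter of efficiency and not an error that invalidates the design.

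**What to change.** For each outcome, replace the complete-case repeated-measures MANOVA with a linear mixed model fitted by REML. Use fixed effects for phase, time and phase × time (two time levels for strength) and Kenward-Roger degrees of freedom, and include every valid session of eligible participants. Use an unstructured within-participant covariance where it converges. Otherwise use random intercepts for participant and for participant-by-day, and state that order of fallback in advance. Keep the complete-case MANOVA as a sensitivity analysis.

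The change needs new analysis wording and no new data or participants. The downside is reliance on data missing at random and on a modelled covariance in a small sample. The fallback structure is more restrictive than the covariance the MANOVA allows, and under it the G*Power calculation would no longer match the primary test exactly. The sensitivity analysis gives a check on both. The hormone exclusion rule stays as it is under this change.

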### Inclusion criteria (must have all the following):

- Female (assigned at birth)
- Aged 18-30
- Tier 2 athlete which requires the participants to identify with a specific sport, train with a purpose to compete, regularly train ~3 times per week and compete at a local level (for example being a member of a BUCS sport and competing regularly with that sport)
- Regular menstrual cycle – considered between 21–35-day cycles with at least 9 periods a year.

### Exclusion criteria (cannot have any of the following):

- The current/previous (in the last 3 months) use of any contraceptive method that alter the menstrual cycle
- The use of the emergency contraceptive pill either 3 months prior to the study or during the study
- Diagnosis of menstrual disorders including (but not exclusively) endometriosis and PCOS
- A formal diagnosis of sleep disorders such as insomnia
- Consume  $>400\text{mg/day}$  of caffeine
- A musculoskeletal injury in the past 3 months
- A formal diagnosis of neurological or psychiatric disorders such as ADHD, ASD, Dyslexia or schizophrenia
- Taking prescribed medication that may affect sleep for example stimulants such as Methylphenidate

- No regular night shift work
- No trans-meridian travel within 10 days of their expected participation dates (travel that will cause jetlag)
- Have given blood in the last 12 weeks – this is not strictly an exclusion; participants will just need to wait until after 12 weeks before taking part in the study

Following confirmation from the participant that they meet all inclusion criteria, they would be invited for a pre-screening and familiarisation visit to the Human Performance Laboratory (HPL). Participants must refrain from alcohol, drugs and caffeine 24 h before the screening and must attend the screening in active wear.

Participants will be provided with an information sheet on arrival, outlining the study, followed by a consent form that must be signed before continuing. A questionnaire pack entitled “Screening questionnaire pack” must then be completed by each participant. The screening questionnaire pack includes 4 sections: ‘Section 1 – The ACSM’, ‘Section 2 – The menstrual cycle questionnaire’ and ‘Section 3 – The Composite Morningness questionnaire’ (Smith *et al.*, 1989) and ‘Section 4 – daily caffeine consumption questionnaire’.

**Section 1** assesses the risk factors of each participant, asking for family history, health conditions, and measuring resting blood pressure, anthropometrics, blood analysis and checking for atrial fibrillation. Each participant must pass this assessment prior to continuing. If at this stage, the participants answer’s require medical clearance, they will be asked to provide this before continuing with the study. If a participant does not receive medical clearance, they will no longer be able to take part in the study and be provided with a debrief sheet. Throughout the study, if a participant presents as unable to continue in the study or wishes to withdraw from the study, they too will be provided with a debrief sheet.

**Section 2** is further divided into part A and B. Part A will ensure the participants are eligible for the study by asking them about the regularity of their menstrual cycle, as well as asking when their next cycle starts (the first day of bleeding) which will also inform the possible dates the participant can carry out the testing days. Part B contains the menstrual distress questionnaire (MEDI-Q), an evaluation tool of a participant’s menstruation-related distress, investigating participants experience of pain, discomfort, psychic and cognitive changes, gastrointestinal symptoms and changes in physiological function during their periods over the last 12 months (Vannuccini *et al.*, 2021).

**Section 3** assesses the participants morningness chronotype by asking questions surrounding their ideal wake-sleep routine, how they would feel if they had to rise in the early morning and how well they function after waking. From this, their chronotype can be determined using a scoring system of 1-5 on each option of the questionnaire; morning type (44 and above), intermediate type (22-43) and evening type (22 and less; Shahid *et al.*, 2011).

**Section 4** assesses how much caffeine the participant typically consumes day-to-day; asking what form of caffeine they consume (drinks such as tea or tablets) and the quantity.

Familiarisation of the executive function task and muscle strength tests will follow, to allow participants to practice the tests. The familiarisation visit must be conducted 1-2 weeks before the first testing visits to minimise learning effects.

Participants will be provided with five Luteinising hormone (LH) ovulation strips (Easy@Home, Easy Healthcare Corporation, IL, USA) to take home and use three to four days prior to expected ovulation date (known by self-tracking of their menstrual cycle). These strips require participants to urinate onto the strip and wait 2-3 minutes (min) for the indicator to appear. For a positive test, the indicator line must show up darker than the control line. LH is always present in the body however there is a rise in

**Commented [CG1]:** Re screening - at the screening visit I'd suggest you ask [name] to have a look at the participant's veins.

Some young females can be very tricky to get blood from. It doesn't mean we need to exclude but might be worth having extra help in the lab - we need to be confident we're getting blood from anyone who participates...

**Commented [CG2]:** I would insert a table here or where appropriate that says (i) what we're going to measure and (ii) in what biofluid and (iii) why

e.g. Oestrogen (E2) in blood at morning visit of visit 1 and 2 to distinguish follicular vs luteal phase

Progesterone - blood

LH - urine?

FSH?

LH levels 12-36 h prior to ovulation and therefore the positive test on the strip is an indicator of when ovulation will occur for the participant. If a participant does not get a positive test, they will be sent the debrief sheet and will no longer be able to partake in the study as some females do not ovulate (anovulation/ oligo-ovulation) and therefore are not eumenorrheic (Mihm *et al.*, 2011). Participants in this study will follow a similar structure to the best practice highlighted by Verhagen *et al.*, (2025) in which one cycle of the following is required: self-reporting the onset of menses to schedule phase 1 testing, a day 1,2,3 or 4 blood sample for the determination of  $\beta$ -oestradiol and progesterone to confirm phase 1, daily LH urine sticks from 5 days before estimated day of ovulation until the LH surge to schedule phase 2 testing, and a blood sample for the determination of progesterone ( $\geq 16 \text{ nmol.L}^{-1}$ ) +7 days ( $\pm 1$ ) days after confirmation of the LH surge to confirm phase 4 testing.

24 h before both testing visits, participants will be asked to refrain from alcohol and drug consumption and retire before 23:00 h. On the day of both tests, participants will be asked to wake at 06:00 h and arrive at HPL fasted and having consumed no caffeine. Participants will visit the laboratory 3 times; 07:00, 12:00 and 18:00 h and carry out the same battery of tests at each time. On the first visit, participants will be provided with a food diary, asking them to record exactly what they ate and when, so that this can be replicated on the second test day to reduce variability in individual data. Participants would be asked to arrive at 12:00 and 18:00 h having fasted for 3 h prior; they would be told to eat immediately after each testing session at 08:00, 13:00 and 19:00 h to limit the thermic effect of food (TEF) on core body temperature (Reed and Hill, 1996).

**Commented [CG3]:** as discussed yesterday it might be better to specify when they should eat rather than when not - just a thought

Test day protocol:

Figure 1 shows a schematic of the research design and the experimental procedure. The participants would perform the full process described above at 07:00 and 18:00 h, whilst at 12:00 h participants would carry out all steps except the strength measures to reduce the fatiguing effect on these measures.

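### LH strip testing has three start days, two surge lead times and five strips for open-ended daily testing, so some ovulating women can be removed for lack of a positive strip

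*Protocol*

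**What the plan says.** The LH instructions are in two places: the unnumbered text on ovulation strips, which follows the eligibility and screening text under the Exclusion criteria heading, and the luteinising hormone row of Table 1.

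- **Supply:** "Participants will be provided with five Luteinising hormone (LH) ovulation strips".
- **Start day, first statement:** "use three to four days prior to expected ovulation date". The expected date comes from the participant's own cycle tracking.
- **Start day, second statement, with frequency and stop rule:** "daily LH urine sticks from 5 days before estimated day of ovulation until the LH surge".
- **Start day, third statement (Table 1):** "Carried out 5 days prior to expected the LH surge which occurs 24-48 hours prior to ovulation".
- **Surge lead time in the text:** a rise in "LH levels 12-36 h prior to ovulation". Table 1 gives 24-48 h.
- **Consequence:** "If a participant does not get a positive test, they will be sent the debrief sheet and will no longer be able to partake". The reason given is "as some females do not ovulate (anovulation/ oligo-ovulation) and therefore are not eumenorrheic".
- **Sequence:** the scheme is described as one "in which one cycle of the following is required: self-reporting the onset of menses to schedule phase 1 testing", then the Phase 1 blood sample, the LH sticks, and the Phase 4 blood sample 7 (±1) days after the surge.

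**The concern.** The strip result decides whether a woman stays in the study, yet the instructions for obtaining it disagree on when to start. The fixed supply also does not match the open-ended stop rule. If the strips run out before the surge, a woman who ovulates has no positive test and is removed on the ground that some women do not ovulate.

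Without a detected surge Phase 4 cannot be scheduled in that cycle, so some removal rule is needed. The problem is applying it after a window that may close too early, and reading the result as evidence about ovulation.

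The phase comparison is within-woman, so what is at stake is the number of completers and the population to which the results apply. Women who ovulate later than they predict are the ones mainly lost. If the scheme is read as one cycle, the strips come after Phase 1 testing, and each such removal also wastes a completed Phase 1 test day.

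**Working it through.** The protocol gives no detection rate, so there is no figure of its own to reproduce. The first two steps use only its stated numbers; the later steps add a labelled assumption.

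**1. Start days on one scale (day 0 = expected ovulation).**
- First statement: day -3 or -4.
- Second statement: day -5.
- Table 1: 5 days before a surge that is itself 1 to 2 days before ovulation, so day -6 (24 h lead) or day -7 (48 h lead).

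No two coincide. The two lead times overlap only at 24-36 h.

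**2. What five strips cover at one a day (last strip = start + 4).**

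| Start | Days covered | On-time surge |
|---|---|---|
| -3 | -3 to +1 | covered |
| -4 | -4 to 0 | covered |
| -5 | -5 to -1 | covered with a 24 h lead; with a 12 h lead (day -0.5) it falls after the last strip |
| -6 (Table 1, 24 h) | -6 to -2 | surge on day -1, one day after the last strip |
| -7 (Table 1, 48 h) | -7 to -3 | surge on day -2, one day after the last strip |

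**3. Illustration with error in the predicted date.** Assumptions, not protocol figures: X = actual minus expected ovulation day, normal with mean 0 and standard deviation SD, rounded to whole days. The strip is positive either on one day (X-1) or on two days (X-2 and X-1). With first strip s and last strip L:

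- one-day detection = Φ((L+1.5)/SD) - Φ((s+0.5)/SD)
- two-day detection = Φ((L+2.5)/SD) - Φ((s+0.5)/SD)
- early miss (surge before the first strip) = Φ((s+0.5)/SD)
- late miss = the remainder

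Example, s = -5, L = -1, SD 2: one-day Φ(0.25) - Φ(-2.25) = 0.586; two-day Φ(0.75) - Φ(-2.25) = 0.761.

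Five strips (ranges run from the one-day to the two-day model):

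| Start | Detected, SD 1 | Detected, SD 2 | Detected, SD 3 | Late miss, SD 2 | Early miss, SD 2 |
|---|---|---|---|---|---|
| -3 | 0.988-0.994 | 0.789-0.854 | 0.595-0.676 | 0.106-0.040 | 0.106 |
| -4 | 0.933-0.994 | 0.733-0.854 | 0.570-0.676 | 0.227-0.106 | 0.040 |
| -5 | 0.691-0.933 | 0.586-0.761 | 0.499-0.625 | 0.401-0.227 | 0.012 |
| -6 | 0.309-0.691 | 0.398-0.596 | 0.400-0.533 | 0.599-0.401 | 0.003 |

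Table 1 with its 48 h lead (start -7, one positive day at X-2) gives 0.398 at SD 2, the same as with the 24 h lead.

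**4. Effect of a longer window.** As an example only, testing through day +3 (L = 3):

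| Start | Strips | Detected, SD 2 | Detected, SD 3 |
|---|---|---|---|
| -3 | 7 | 0.882-0.891 | 0.731-0.764 |
| -4 | 8 | 0.948-0.957 | 0.812-0.845 |
| -5 | 9 | 0.976-0.985 | 0.866-0.900 |

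Late misses fall to at most 0.012 at SD 2 and to 0.033-0.067 at SD 3. More strips at the end cannot recover early misses.

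**5. Sensitivity to the timing model.** Treat the surge as a continuous time 24 h before ovulation, with positivity lasting about one day. The miss rates at SD 2 are then 23%, 33% and 51% for starts -3, -4 and -5, and 69% for Table 1. These are worse than in step 3 at every start day, and the ordering is the same.

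**6. Context.** The sample-size paragraph seeks 30 participants against a minimum of 24, so it tolerates 1 - 24/30 = 20% loss from all causes, including the exclusions after testing on hormone levels.

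**The case against.** The strongest reply has five parts.

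- **Table 1 is loose.** The row is garbled, sits in a purpose column, and may only be a careless restatement of the 5-day rule. That is possible, and the lowest detection figures come from reading it literally. The main text alone still has two start days and a supply that does not fit its stop rule.
- **The daily rule is borrowed.** It is presented as similar to a cited best practice, and it mentions scheduling Phase 2, which this study does not test. The sentence nevertheless applies the scheme to participants in this study.
- **The lead time has no operational effect**, since Phase 4 is timed from the detected surge. This holds for Phase 4 scheduling. It does not hold for Table 1, where the start day is counted back from the surge. It remains the weakest of the discrepancies.
- **Removal after exactly five strips is inferred.** The text does not forbid further strips. But it provides five, and it describes no resupply, extension or other check before removal. Under the 3-4 day start, an on-time surge is covered; the shortfall there concerns dates that were predicted wrongly.
- **The percentages are assumed.** This is correct. They vary widely with the SD, the days of positivity and the timing convention, and they should not be quoted as expected rates. At SD 3 even the longer window detects only 73-90%.

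The protocol's allowance for loss also softens the consequence, but it does not make the instructions consistent.

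**Conclusion.** The concern holds. The contradictions in start day and lead time, and the mismatch between five strips and testing until the surge, are in the text and need no assumption. It also follows from the protocol's own figures that five daily strips can end before an on-time surge: under Table 1 read literally, and under the 5-day start with a short lead. Some ovulating women can therefore be removed.

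How many is unknown. In the illustration at an assumed SD of 2 days, late misses, the part that more strips could recover, are 4-11 points from day -3, 11-23 from day -4, 23-40 from day -5 and 40-60 under Table 1. These figures rest on normal prediction error, one strip a day and one or two positive days.

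The effect is on completers, wasted Phase 1 days (if all is done in one cycle) and applicability, not on the validity of the within-woman phase contrast. It should be fixed before recruitment.

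**What to change.** 1. Reconcile the strip text and Table 1 to one start day and one surge lead time.
2. State a testing window that extends past the expected ovulation date, and supply enough strips for daily testing throughout it, so that the protocol's own stop rule can be followed.
3. Apply removal for lack of a positive strip only after that window has been tested in full. Record the reason as *LH surge not detected, Phase 4 cannot be scheduled*, and not as evidence that the participant does not ovulate.

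**Cost:** about two to four more home strips per participant (7-9 in place of 5 if, for example, the window ends at day +3) and wording changes in two places. No extra visits or cycles are needed; a repeat cycle is optional and not part of this fix. Women who surge before the first strip would still be missed, and if self-tracked dates are poor (SD 3) some late surges would be too.

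### The protocol implies that Phase 1 is always tested before Phase 4 and mentions no counterbalancing; if so, the phase effect cannot be separated from test-day order.

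*Protocol*

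**What the plan says.** Phase is one of the two independent variables and is compared within one group of participants (Protocol, opening section).

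- **Scheduling.** The paragraph on LH strips, under the exclusion-criteria heading, says that "one cycle of the following is required: self-reporting the onset of menses to schedule phase 1 testing". A blood sample on days 1 to 4 confirms Phase 1. LH testing follows, and a progesterone sample is taken 7 (±1) "days after confirmation of the LH surge to confirm phase 4 testing".
- **Session list.** The research design section gives "2 experimental sessions i) Phase 1 and ii) Phase 4".
- **Learning.** The only stated control is familiarisation: "The familiarisation visit must be conducted 1-2 weeks before the first testing visits to minimise learning effects".
- **Repetition within a day.** The battery is run at 07:00 and 18:00, and "at 12:00 h participants would carry out all steps except the strength measures to reduce the fatiguing effect on these measures". The Flanker task is therefore done three times on each test day.
- **Sample size.** G*Power "indicated a minimum sample size of 24, however, to account for any potential data loss or dropouts" the study aims for 30.

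No available text mentions randomised, alternated or counterbalanced phase order, and no sequence groups are described.

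**The concern.** In a two-condition within-participant comparison, a fixed order means that anything changing between the first and second test day is counted as an effect of the condition. Here the obvious candidate is practice on the Flanker task. By the time Phase 4 is tested, each participant has had the familiarisation visit and three further runs. Any gain left over would be read as an effect of high progesterone, or would hide a real decrement in Phase 4.

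The protocol recognises learning effects, but familiarisation reduces them without removing the confounding. A SAP cannot repair this either, because the order is settled when participants are booked.

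**Working it through.** **1. The plan's own figure.** Inputs from the opening section: f = 0.25, alpha 0.05, power 80%, one group, 3 times × 2 phases = 6 measurements. The correlation is not stated; 0.5 is assumed. For a within-factor MANOVA, λ = N·m·f²/(1−ρ) = 24 × 6 × 0.0625/0.5 = 18, with df 5 and 19. Power is 0.825 at N = 24 and 0.799 at N = 23, so 24 reproduces. It has no bearing on the confounding, which does not depend on N.

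**2. Implied order.** Phase 1 falls on days 1 to 4 of the cycle, and Phase 4 falls 6 to 8 days after the LH surge. Within one cycle Phase 1 must come first, which agrees with the session list.

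**3. Can phase and test day be separated?** Take a design matrix with 24 participant columns, one phase column and one test-day column (26 in all).

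| Order | Rank |
|---|---|
| Phase 1 always first | 25 |
| 12/12 split of starting phase | 26 |
| 15/9 split | 26 |

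Under fixed order the phase and test-day columns are identical.

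**4. False phase effect (illustration).** Paired contrast at one time of day, two-sided noncentral t, no true phase effect. The shift δ is in SDs of the paired difference and is assumed. The noncentrality is δ√N.

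| δ | N = 24 (df 23) | N = 30 (df 29) |
|---|---|---|
| 0.1 | 7.6% | 8.3% |
| 0.2 | 15.6% | 18.5% |
| 0.3 | 29.1% | 35.5% |

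**5. Masking (illustration).** This applies the protocol's f = 0.25 to the two-level phase contrast: dz = 2f/√(2(1−ρ)). A practice gain opposite to the true effect leaves dz − δ. Power at N = 24:

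| Assumed ρ | dz | δ = 0 | 0.1 | 0.2 | 0.3 |
|---|---|---|---|---|---|
| 0.3 | 0.42 | 51% | 33% | 18% | 9% |
| 0.5 | 0.50 | 65% | 47% | 29% | 16% |
| 0.7 | 0.65 | 86% | 73% | 55% | 37% |

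**6. Power after counterbalancing.** With a test-day term, SE = 0.5·√(1/nA + 1/nB) and df = 22. For dz = 0.5 at N = 24, power is 65.0% without the term. With it, power is 64.9% at 12/12, 63.6% at 14/10, 62.1% at 15/9 and 59.8% at 16/8. If 30 are randomised 15/15 and six are lost at random, the hypergeometric probability of 13/11 or better is 0.349 + 0.483 = 83%; of 15/9, 1.7%.

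**7. Gaps between test days.** Assume menses 14 days after the surge. In a 28-day cycle the surge is on day 14 and Phase 4 on days 20 to 22. Phase 1 to Phase 4 is then 20 − 4 = 16 to 22 − 1 = 21 days (9 to 28 days over eligible cycles of 21 to 35 days). Phase 4 to the next Phase 1 is 29 − 22 = 7 to 32 − 20 = 12 days.

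**The case against.** **The order is inferred.** No sentence says every participant is tested in Phase 1 first. The scheduling sentence adapts a cited best-practice source and also uses "daily LH urine sticks from 5 days before estimated day of ovulation until the LH surge to schedule phase 2 testing", a session this study does not have. The session list could simply name two conditions. A margin comment that hormones be measured "in blood at morning visit of visit 1 and 2 to distinguish follicular vs luteal phase" fits the same order but is only a suggestion. The schematic is not available and might show counterbalancing. All this stands, which is why the point is conditional. Even so, this is the only scheduling rule in the text, and a counterbalanced design would conflict with its one-cycle wording.

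**The size is illustrative.** The practice gains have no source in the documents, the calculation is a paired test at one time of day and not the planned MANOVA, and f = 0.25 is not stated as an effect of phase. This also stands; the confounding does not depend on these figures. The related point that practice may slow across runs (1 against 4, 2 against 5, 3 against 6) adds to the concern, because unequal shifts would also reach the phase-by-time interaction.

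**The scope is narrow.** The mechanism is practice on the Flanker task. None is shown for EEG, and strength tests are also familiarised. This is accepted.

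**Counterbalancing has costs.** Half the participants would be compared across two cycles, with unequal gaps and a tight familiarisation window. These costs are real and are set out with the fix.

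**Conclusion.** The concern holds in conditional form. The available text implies Phase 1 then Phase 4 and says nothing of counterbalancing. If that order is followed, the phase main effect is fully confounded with test-day order at any sample size. The phase-by-time interaction is affected only if the order effect differs by time of day.

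The amount of bias is unknown. Under assumed residual gains of 0.1 to 0.3 SD of the paired difference, the 5% test of phase would reject in 7.6% to 29.1% of studies with 24 participants and no true effect. This should be fixed before testing starts, since it cannot be corrected afterwards. Confidence is medium, because the order is inferred and the schematic could not be seen.

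**What to change.** State the phase order in the scheduling paragraph and the research design section. Preferably, randomise the starting phase 1:1 in small blocks: either Phase 1 then Phase 4 in the same cycle, or LH-timed Phase 4 then Phase 1 at the next menses. Amend the one-cycle wording to match and include test-day order in the model.

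The cost is a protocol amendment and a randomisation list, with no extra participants, visits or samples. The power loss is negligible unless dropouts and post-test hormone exclusions leave the sequences badly unbalanced. Three further costs should be weighed:

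- Half the participants finish in the next cycle.
- The unequal gaps mean carry-over is not fully removed. If practice gains differ by 0.1 SD between sequences, the remaining bias is 0.05 SD and the error rate 5.6% at 12/12.
- For those starting in Phase 4, familiarisation must be timed from predicted ovulation. Keeping the 1–2 week rule for a test on any of days 6 to 8 after the surge, and handing out strips in time, puts it 12–13, 11–13 or 9–13 days before surge day +7 (assuming ovulation one day after the surge). Which applies depends on which of the protocol's three wordings for starting the strips is used. With the narrowest window, a surge three days late breaches the rule for a day +7 test.

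If these costs are judged too high, keep the fixed order, say so plainly, and describe the phase main effect as phase plus test-day order. That costs a sentence or two.
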